### **8.0 Adverse events**

---

An adverse event (AE) is any untoward medical occurrence in a patient receiving study treatment and which does not necessarily have a causal relationship with this treatment. An AE can therefore be any unfavorable and unintended sign (including a clinically significant abnormal laboratory finding), symptom, or disease temporally associated with the use of an experimental intervention, whether or not related to the intervention.

Progression of the cancer under study or events that are unequivocally due to disease

---

progression should not be reported as an AE during the study (unless it is considered to be drug related by the investigator).

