### **2.2 Secondary:**

- To evaluate the occurrence of adverse events using the National Cancer Institute Common Terminology Criteria for Adverse Events (CTCAE) version 4.03.10
- To evaluate complete response defined as no emesis and no use of rescue medication for 5 days after Akynzeo® administration.
- To characterize 24-hour CINV using a modified MASCC Antiemesis Tool (MAT). (**Appendix 1**)
- To evaluate 5-day health related quality of life recall using the Functional Living Index for Emesis (FLIE) scale.
- To evaluate healthcare resource utilization as defined by the number of emergency room visits, hospitalizations, and infusion center visits encounters regarding signs/symptoms associated with CINV over the seven-day study period.
- To evaluate the occurrence of refractory CINV using CINV risk assessment at follow up day 7 compared to treatment day 1.

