#### **3.1 Inclusion Criteria**

1. Adults greater than or equal to 18 years old.
2. Must have a histologically confirmed cancer diagnosis.
3. Must have refractory CINV defined as nausea and/or vomiting that occurs after the first cycle of cancer targeted therapy despite guideline-based prophylaxis and after first-line rescue medication with either a dopamine receptor antagonist, steroid, and/or benzodiazepine.
4. Eastern Cooperative Oncology Group (ECOG) performance status less than or equal to 2.
5. Life expectancy greater than 3 months.
6. Corrected serum calcium level less than or equal to 10.5 mg/dL.
7. Women of child-bearing potential must agree to use adequate contraception (hormonal or barrier method of birth control; abstinence) prior to study entry, for the duration of study participation, and for 14 days following completion of therapy.  
A woman of child-bearing potential is any female (regardless of sexual orientation, having undergone a tubal ligation, or remaining celibate by choice) who meets the following criteria:
  - a. Has not undergone a hysterectomy or bilateral oophorectomy; or
  - b. Has not been naturally postmenopausal for at least 12 consecutive months (i.e., has not had menses at any time in the preceding 12 consecutive months)
8. Women of child-bearing potential must have a negative pregnancy test prior to initiating study treatment.
9. Ability to understand and willingness to sign a written informed consent.

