## 8.1 Adverse Event Monitoring

Adverse event data collection and reporting, which are required as part of every clinical trial, are done to ensure the safety of subjects enrolled in the studies as well as those who will enroll in future studies using similar agents. Adverse events are reported in a routine manner at scheduled times during a trial. Additionally, certain adverse events must be reported in an expedited manner to allow for optimal monitoring of patient safety and care.

As far as possible, each adverse event should be evaluated to determine:

- duration (start and end dates)
- severity (grade)
- seriousness
- relationship to study agent
- action taken (i.e., none, study agent modification, medical intervention)
- outcome (i.e., resolved without sequelae, resolved with sequelae, ongoing)

Adverse events monitoring begins at the time of informed consent signature and ends within 30 days of the last administration of the study drug.

All patients experiencing an adverse event, at least possibly related to the drug, will be monitored until:

- the adverse event resolves or the symptoms or signs that constitute the adverse event return to baseline;
- any clinically significant abnormal laboratory values have returned to baseline;
- there is a satisfactory explanation other than the study drug for the changes observed; or
- death.

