### 9.3 Secondary aims

Secondary outcome measures including (1) the evaluation of adverse events utilizing the NCI CTCATE v4.03, (2) complete response (no emesis and no rescue medication use), (3) characterization of 24-hour CINV using the MAT, (4) five-day health related quality of life utilizing the FLIE, and (5) healthcare resource utilization (emergency room visits, hospitalizations, and infusion center visits over seven days).

- (1) Adverse events will be recorded in detail and the number of events will be described using n and percent. The severity will be described using means (SD) and medians (IQR) of the adverse event grade (which ranges 0-5).
- (2) The proportion of patients experiencing complete response will be described with descriptive statistics (n and percent) as well as by using a one-sample confidence interval for proportions, applying the normal approximation to the binomial distribution. In addition, a one-sample z test for proportions will be used to determine if the complete response rate in this sample is significantly different than the 90% seen in previous studies.
- (3) CINV will be analyzed using the MAT. The MAT consists of 8 distinct items, 4 of these items are binary and will be described using n and percents the other 4 items are continuous (ranging from 0-10) and will be described using mean and SD. Binary variables will also be described using one-sample confidence intervals for proportions (as described in #2 above) and continuous variables will be described using one-sample confidence intervals for means.
- (4) Quality of life will be analyzed as a binary response, impact on quality of life vs no impact, a score of less than 54 on the FLIE domain scores and a score of less than 108 on the total score indicates an impact on quality of life. Each domain score, and the total score, will be analyzed separately using a 95% confidence interval to describe the proportion of participants with impacted QoL.
- (5) Healthcare resource utilization will be assessed by recording the number of emergency room visits, hospitalizations (with length of stay), and infusion center visits. Each healthcare utilization will be categorized with respect to whether it was specifically related to nausea and vomiting during the seven-day follow up period. A table summarizing the number of each type of utilization related to nausea and vomiting will be provided.

- 

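### Nausea and vomiting, the condition being treated, can enter the adverse event summary, so its count and mean grade partly reflect treatment failure and not tolerability

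*Combined protocol and SAP*

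**What the plan says.** **Definition.** Section 8.0 covers any unfavourable "symptom, or disease temporally associated with the use of an experimental intervention, whether or not related to the intervention". Its one exception begins "Progression of the cancer under study or events that are unequivocally due to disease" and concerns cancer progression. Nausea and vomiting are not mentioned.

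**Population.** Section 3.1, item 3: "Must have refractory CINV defined as nausea and/or vomiting that occurs after the first cycle of cancer targeted therapy despite guideline-based prophylaxis". Section 6.0 has refractory CINV confirmed before the capsule is taken.

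**Efficacy.** Section 2.2: "To evaluate complete response defined as no emesis and no use of rescue medication for 5 days after Akynzeo". Nausea is not part of that definition. The MAT (5.5.2) and FLIE (5.5.3) measure nausea and vomiting again.

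**Safety analysis.** Section 9.3(1): "Adverse events will be recorded in detail and the number of events will be described using n and percent". Severity is to be given as the mean and median grade. The synopsis says the same.

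**Window.** Section 8.1: "Adverse events monitoring begins at the time of informed consent signature", and it runs to as late as 30 days after dosing. The Schedule of Events marks adverse event monitoring from Day 1, and Section 7.0 starts the daily safety assessments on Day 1.

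**The concern.** Adverse event occurrence is the first secondary objective, and the trial has no control arm against which background nausea and vomiting could be set. Daily calls ask about any adverse event (Section 5.1), so continuing CINV is likely to be mentioned. If it is recorded, a subject who vomits on Day 2 counts as a complete-response failure and adds an event and a grade to the safety summary. A subject with headache alone also adds an event and a grade. Nothing planned in 9.3(1) separates the two.

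The safety summary would then rise when the drug fails and fall when it works. Section 5.3 intends to use the secondary results to shape a larger study, so a tolerability figure that partly repeats the efficacy result would be carried forward.

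**Working it through.** **Does any other section close the gap?**

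- Section 8.1 mentions baseline only as an end to follow-up: "the adverse event resolves or the symptoms or signs that constitute the adverse event return to baseline". It does not decide whether an event exists.
- Section 8.3 sets aside admissions for an existing condition that is no worse, but only for the serious-event definition.
- Relatedness could separate events, but Section 8.4 has two levels and Section 9.4 has five, and 9.3(1) uses neither.
- Section 5.0 and the Schedule of Events place MAT and FLIE completion after prophylaxis, following consent. With a start at consent, the qualifying episode can fall inside the monitoring window.

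None of these corrects 9.3(1).

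**How large could the effect be?** The plan gives no expected adverse event rate, so there is no figure to reproduce. Its 80% power statement concerns the completion endpoint and is not involved.

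Inputs:

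- N = 50 (Section 4.1).
- Complete response (CR): 90% is the benchmark in 9.3(2). 70% is the success rate quoted in Section 1.2 for a refractory population, with another drug and another definition. 50% and 30% are assumed.
- Share of subjects with some other adverse event (o): not given; assumed independent of response.
- Every non-responder is assumed to have recorded nausea or vomiting.

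*Per subject.* Any-event rate = 1 − CR × (1 − o). For example, 1 − 0.70 × 0.80 = 0.44. The ratio to o is in brackets.

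| CR | o = 20% | o = 50% | o = 70% |
|---|---|---|---|
| 90% | 28% (1.4) | 55% (1.1) | 73% (1.0) |
| 70% | 44% (2.2) | 65% (1.3) | 79% (1.1) |
| 50% | 60% (3.0) | 75% (1.5) | 85% (1.2) |
| 30% | 76% (3.8) | 85% (1.7) | 91% (1.3) |

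If staff recorded no CINV as an adverse event, the figure would be o itself.

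*Per event.* Section 9.3(1) speaks of events, so take one nausea or vomiting event per non-responder and one other event per affected subject. Share due to nausea or vomiting = 50(1 − CR) / [50(1 − CR) + 50 × o].

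| CR (non-responders) | o = 10% | 30% | 50% | 70% |
|---|---|---|---|---|
| 90% (5) | 50% | 25% | 17% | 12.5% |
| 70% (15) | 75% | 50% | 37.5% | 30% |
| 50% (25) | 83% | 62.5% | 50% | 42% |
| 30% (35) | 87.5% | 70% | 58% | 50% |

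The share runs from 5/40 = 12.5% to 35/40 = 87.5%.

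**The case against.** A reader might infer that every non-responder becomes an adverse event. The documents do not support that. Section 5.4 permits standard breakthrough drugs, so a subject can fail on rescue alone without vomiting. Conversely, a complete responder may still have nausea that is recorded. The overlap is real but not one to one, and the illustration can err in either direction.

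A reader might also infer that the safety table mostly restates efficacy. That depends on two unknown rates. At the plan's own 90% benchmark the nausea and vomiting share never exceeds half over the range shown. Subjects are on cancer treatment, and events of any cause are collected for up to 30 days, against 5 days for response, so other events may be common.

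Nor can one say that the rate approaches 100% because everyone qualifies with CINV. That needs the start at consent in 8.1. Section 8.0 speaks of a patient on study treatment, and the Schedule of Events starts on Day 1.

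Two further points are fair. Section 9.3(1) names no per-subject any-event rate, so the first table describes a statistic the plan does not define. It also does not forbid a listing by CTCAE term, and events are to be recorded in detail and graded. Counting unchanged baseline nausea is therefore one reading of a silent text, not the only one. What remains is that the plan commits to no breakdown, and a pre-dose grade that was never recorded cannot be recovered later.

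**Conclusion.** The concern holds as a gap in the planned summary. The definition in 8.0 admits nausea and vomiting, 9.3(1) does not separate them, and no other section does so. The adverse event count and mean grade can therefore partly reflect treatment failure, to a degree that also depends on how staff record persisting symptoms.

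The size is not fixed by the documents. On the stated assumptions, with other events in 20% of subjects, the any-event rate is 28% to 76% as complete response falls from 90% to 30%. That is 1.4 to 3.8 times the rate of other events. With other events in 70% of subjects the ratio is 1.0 to 1.3. These figures are illustrations, not estimates, and they do not show that the summary is uninformative about tolerability.

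The start of monitoring (8.1 against the Schedule of Events) and the relatedness scale (8.4 against 9.4) are separate inconsistencies that add to the problem. The primary endpoint, sample size and power are unaffected.

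**What to change.** 1. In 9.3(1) and the synopsis, report adverse event counts and grades by CTCAE term and relatedness. Put nausea, vomiting and retching in a separate block, and show the overall count and grade summary with and without that block. The figures without it then do not depend on how persisting CINV was recorded.
2. Record the pre-dose grade of these symptoms at the Day 1 safety assessment already scheduled, so that worsening can be shown within the block. A worsening rule cannot do the job alone: Section 7.0 links dosing to C2D1, and a subject whose pre-dose grade is 0 would count as worsened with any later vomiting.
3. Reconcile the start of adverse event monitoring in 8.1 with the Schedule of Events, and the two-level relatedness scale in 8.4 with the five-level scale in 9.4.

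Individual capture and serious or expedited reporting stay as they are. The cost is a few sentences, slightly more coding, one grade at an existing assessment and one extra table block.

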## 8.1 Adverse Event Monitoring

Adverse event data collection and reporting, which are required as part of every clinical trial, are done to ensure the safety of subjects enrolled in the studies as well as those who will enroll in future studies using similar agents. Adverse events are reported in a routine manner at scheduled times during a trial. Additionally, certain adverse events must be reported in an expedited manner to allow for optimal monitoring of patient safety and care.

As far as possible, each adverse event should be evaluated to determine:

- duration (start and end dates)
- severity (grade)
- seriousness
- relationship to study agent
- action taken (i.e., none, study agent modification, medical intervention)
- outcome (i.e., resolved without sequelae, resolved with sequelae, ongoing)

Adverse events monitoring begins at the time of informed consent signature and ends within 30 days of the last administration of the study drug.

All patients experiencing an adverse event, at least possibly related to the drug, will be monitored until:

- the adverse event resolves or the symptoms or signs that constitute the adverse event return to baseline;
- any clinically significant abnormal laboratory values have returned to baseline;
- there is a satisfactory explanation other than the study drug for the changes observed; or
- death.

## 8.2 Severity

All adverse events will be graded according to the NCI CTCAE version 4.03. The CTCAE v4.03 is available at <http://ctep.cancer.gov/reporting/ctc.html>

Per CTCAE v 4.03 when no predefined grading is available, the severity of an AE is graded as follows:

- Grade 1 Mild; asymptomatic or mild symptoms; clinical or diagnostic observations only; intervention not indicated.
- Grade 2 Moderate; minimal, local or noninvasive intervention indicated; limiting age-appropriate instrumental ADL\*.
- Grade 3 Severe or medically significant but not immediately life-threatening; hospitalization or prolongation of hospitalization indicated; disabling; limiting self-care ADL\*\*.
- Grade 4 Life-threatening consequences; urgent intervention indicated.
- Grade 5 Death related to AE.
- \*Instrumental ADL refer to preparing meals, shopping for groceries or clothes, using the telephone, managing money, etc.
- \*\*Self care ADL refer to bathing, dressing and undressing, feeding self, using the toilet, taking medications, and not bedridden.

---

### 8.3 Seriousness

A “serious” adverse event (SAE) is defined in regulatory terminology as any untoward medical occurrence that:

1. Results in death. If death results from (progression of) the disease, the disease should be reported as event (SAE) itself.
2. Is life-threatening. The patient was at risk of death at the time of the event; it does not refer to an event that hypothetically might have caused death if it were more severe.
3. Requires in-patient hospitalization or prolongation of existing hospitalization.  
Note: Hospitalization (including hospitalization for an elective procedure) for a pre-existing condition that has not worsened does not constitute a serious adverse event.
4. Results in persistent or significant disability or incapacity.
5. Is a congenital anomaly/birth defect
6. Is an important medical event.
  - Any event that does not meet the above criteria, but that in the judgment of the investigator jeopardizes the patient, may be considered for reporting as SAE. The event may require medical or surgical intervention to prevent one of the outcomes listed in the definition of “Serious Adverse Event“.

### 8.4 Relationship

The relationship to the IP of each AE/SAE will be evaluated by the investigator using the following levels:

- **Not related:** The temporal relationship of the clinical event to the administration of IP makes a casual relationship unlikely; and other drugs, therapeutic intervention or underlying conditions provide a sufficient explanation for the observed event.
- **Related:** The temporal relationship of the clinical event to the administration of the IP makes a casual relationship possible; and other drugs, therapeutic interventions or underlying conditions do not provide sufficient explanation for the observed event. A clear-cut temporal association with improvement on cessation of the study drug or recurrence upon re-challenge may also be observed

### 8.5 Prior experience

Expected events are those that have been previously identified as resulting from administration of the agent. An adverse event is considered unexpected, for expedited reporting purposes only, when either the type of event or the severity of the event is not listed in the current known adverse events listed in the agent clinical experience section of this protocol and Akynzeo prescribing information.

### 8.6 Reporting Requirements for Adverse Events

#### 8.6.1 Expedited Reporting

- A. The **Principal Investigator** must be notified within 24 hours of learning of any serious adverse events, regardless of attribution, occurring during the study or within 30 days of the last administration of the study drug.
- B. The **UCSD Human Research Protections Program (HRPP)** and **Moores Cancer Center Data and Safety Monitoring Board (DSMB)** must be notified within 10 business days of “any unanticipated problems involving risk to subjects or others” (UPR).

The following events meet the definition of UPR:

1. Any serious event (injuries, side effects, deaths or other problems), which in the opinion of the Principal Investigator was unanticipated, involved risk to subjects or others, and was possibly related to the research procedures.
2. Any serious accidental or unintentional change to the IRB-approved protocol that alters the level of risk.
3. Any deviation from the protocol taken without prior IRB review to eliminate apparent immediate hazard to a research subject.
4. Any new information (e.g., publication, safety monitoring report, updated sponsor safety report), interim result or other finding that indicates an unexpected change to the risk/benefit ratio for the research.
5. Any breach in confidentiality that may involve risk to the subject or others.
6. Any complaint of a subject that indicates an unanticipated risk or that cannot be resolved by the Principal Investigator.

**C.** The **FDA** must be notified according to the following timelines:

- within 7 calendar days of any unexpected fatal or life-threatening adverse event with possible relationship to study drug, and
- within 15 calendar days of any event that is considered: 1) serious, 2) unexpected, and 3) at least possibly related to study participation.

**D.** A copy of all SAEs will be submitted to **Helsinn's safety designee** using the approved local regulatory form within 24 hours of the Principal Investigator's awareness by email ([[contact]](mailto:[contact])) or [contact]).

### 8.6.2 Routine Reporting Requirements

- A.** The **UCSD HRPP** must be notified of any adverse events that are not unanticipated problems involving risk to subjects or others (non-UPRs) at the time of the annual Continuing Review.
- B.** The **FDA** must be notified of all non-serious adverse events annually at the time of the annual report.
- C.** **Helsinn** will be notified of all non-serious adverse events in summary or line-item form upon Helsinn's request and at the conclusion of the study.

### 8.6.3 Pregnancy Reporting Requirements

The **Principal Investigator** must be notified within 24 hours of any pregnancies occurring in a female patient or a female partner of a male patient along with pregnancy outcomes. Elective abortions without complications should not be considered adverse events unless they were therapeutic abortions. Hospitalization for normal delivery of a healthy newborn should not be considered a significant adverse event. Spontaneous abortions should always be reported as significant adverse events.

The Investigator should follow-up with the study patient or the female partner of the study patient until delivery or termination of pregnancy, even if the patient was withdrawn from the clinical study or the clinical study was completed. Helsinn will be informed of all pregnancy outcomes using the contact information provided above.

---

## 9.0 Statistical Analysis

---

### 9.1 Study Design

Ideally, a phase III placebo controlled trial would be completed to demonstrate the efficacy of Akynzeo® in the refractory CINV. However, data regarding pharmacologic interventions for refractory CINV are lacking. Furthermore, it is not established if intervening in the refractory CINV setting is practically feasible. Consequently, we believe a feasibility study is the necessary first step followed by a larger randomized trial.

### 9.2 Primary outcome measures and sample size

The proposed study is a prospective, single-center, feasibility trial. The primary aim of this study is feasibility – specifically feasibility will be defined as completion of all study procedures over seven days. For the primary aim, we assume an acceptable completion rate from strata of MEC/HEC or tumor types of all study-related procedures would be at least 70%. Assuming a true completion rate of 85%, a sample size of 50 patients would have an 80% power to detect an absolute difference of 15% at Type I error 0.05.

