**STUDY SCHEMA**

**STUDY SUMMARY**

Title	Fixed-Dose Combination of Netupitant and Palonosetron (Akynzeo®) in the Treatment of Refractory Chemotherapy-Induced Nausea and Vomiting
Short Title	Akynzeo® in the Treatment of Refractory CINV
Phase	II
Methodology	Single-arm, single-center, open-label study
Study Duration	The anticipated total study duration is 24 months from fully-executed contract and IRB approval. Individual subject participation is limited to approximately 1 week.
Study Center(s)	UC San Diego (UCSD) Moores Cancer Center UCSD Medical Center - La Jolla
Objectives	
Primary: To determine the feasibility of using a fixed-dose combination of netupitant and palonosetron (Akynzeo®) in the treatment of refractory CINV. For this study, refractory CINV is defined as nausea and/or vomiting that occurs after the first cycle of cancer targeted therapy despite guideline-based prophylaxis and after first-line rescue medication with either a dopamine receptor antagonist, steroid, and/or benzodiazepine.
 
Hypothesis: Feasibility, defined as more than 70% of selected study subjects completing all study related procedures, will be achieved.
 
Secondary:
 
 
• To evaluate the occurrence of adverse events using the National Cancer Institute Common Terminology Criteria for Adverse Events (CTCAE) version 4.03.
 
• To evaluate complete response defined as no emesis and no use of rescue medication for 5 days after Akynzeo® administration.
 
• To characterize 24-hour intervals of CINV using the MASCC Antiemesis Tool (MAT).
 
• To evaluate 5-day health related quality of life recall using the Functional Living Index for Emesis (FLIE) scale.
 
• To evaluate healthcare resource utilization as defined by the number of emergency room visits, hospitalizations, and infusion center visits encounters regarding signs/symptoms associated with CINV over the seven-day study period.
 
• To evaluate the occurrence of refractory CINV using CINV risk assessment at follow up day 7 compared to treatment day 1.
 
 
Exploratory: To determine patient preference for use of Akynzeo® for future planned chemotherapy utilizing a five-point Likert scale

Number of Subjects	50

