### **4.1 Subjects and Centers**

A total of 50 subjects, who are 18 years of age or older, have histologically confirmed cancer, confirmed refractory CINV as defined above, an ECOG performance status 0-2, and normal calcium level will be enrolled on this single-center, single-arm study.

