### **4.2 Study Design**

This is a Phase II, single-center, single-arm, open-label, feasibility trial using a fixed dose combination of netupitant and palonosetron (Akynzeo®) in the treatment of refractory CINV. The primary aim of this study is feasibility, defined as 70% completion rate of all study procedures over 7 days

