## 5.3 Future Directions

If feasibility is achieved on this study, then future plans would include analysis of secondary and exploratory objectives to determine if there are any trends towards a clinically-meaningful and plausible study endpoint, which would be further developed in a larger Phase II study. We have several key palliative care oncology collaborators, and ultimately plan to propose the Phase II concept through a cooperative group such as the [Palliative Care Research Cooperative Group](#) or the [Alliance in Clinical Oncology Trials](#) Symptom Intervention Committee, both of which [name] is an active member.

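### The primary decision rule is not stated: read literally, more than 70% completing is met at 36/50, and that cut-off does not have the Type I error of 0.05 claimed in section 9.2

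*Combined protocol and SAP*

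**What the plan says.** The synopsis, under a label calling it the hypothesis, states: "Feasibility, defined as more than 70% of selected study subjects completing all study related procedures, will be achieved". Section 2.1 repeats this. Section 4.2 words it differently: "The primary aim of this study is feasibility, defined as 70% completion rate of all study procedures over 7 days". Section 9.2, repeated in the synopsis, speaks of an "acceptable completion rate from strata of MEC/HEC or tumor types of all study-related procedures would be at least 70" (per cent), assumes a true rate of 85%, and claims that "a sample size of 50 patients would have an 80% power to detect an absolute difference of 15% at Type I error 0.05".

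No section gives a null hypothesis, a test, its sidedness, a critical count or a confidence-limit rule for the primary outcome. The only test named in section 9 is the z test for complete response, a secondary outcome. Section 5.3 attaches a consequence to the result: "If feasibility is achieved on this study, then future plans would include analysis of secondary and exploratory objectives".

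**The concern.** The wording of the definition counts subjects, so the literal reading is an observed proportion: with 50 subjects, 36 completers (72%) is enough. A Type I error and a power belong to a decision rule, and those quoted in section 9.2 do not belong to that one. They fit a test that treats 70% as the value to be excluded, and such a test needs a count well above 36.

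At stake is the trial's main conclusion. At 36/50 the written definition is met, yet the exact 90% confidence interval for the completion rate runs from 59.7% to 82.2%. If the rule is settled only after the data are in, a count between the two cut-offs can be reported either way.

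**Working it through.** **Inputs.** n = 50 (sections 4.1 and 9.2); reference rate p0 = 0.70 and assumed true rate p1 = 0.85 (section 9.2); Type I error 0.05, sidedness not stated; claimed power 80%.

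**1. Reproducing the plan's figure.** One-sample score z test, with the null variance for the cut-off and the alternative variance for power:

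n = [(z_α·√(p0(1−p0)) + z_β·√(p1(1−p1))) / (p1−p0)]²

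Here √0.21 = 0.458 and √0.1275 = 0.357.

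- One-sided 0.05: [(1.645×0.458 + 0.842×0.357)/0.15]² = 49.4, rounded up to 50. Power at 50 = Φ[(0.15×√50 − 1.645×0.458)/0.357] = Φ(0.86) = 80.5%.
- Two-sided 0.05, same formula: n = 63.9, power at 50 = 67.5%.

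So 50 subjects and 80% power are reproduced by a one-sided 0.05 score test against 70%.

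**2. Exact binomial behaviour of each possible cut-off.** P(X ≥ c), X ~ Bin(50, p):

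| Rule | Cut-off | p = 0.70 | p = 0.85 |
|---|---|---|---|
| At least 70%, observed | 35/50 | 56.9% | 99.8% |
| More than 70%, observed | 36/50 | 44.7% | 99.5% |
| One-sided 95% Wald lower bound above 70% | 40/50 | 7.9% | 88.0% |
| Exact or score one-sided 0.05 test; also two-sided 95% Wald interval | 41/50 | 4.0% | 79.1% |
| Exact or score two-sided 0.05 test | 42/50 | 1.8% | 66.8% |

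The Wald entries come from the limits themselves. The one-sided bound is 0.707 at 40/50. The two-sided lower limit is 0.689 at 40/50 and 0.714 at 41/50. The score statistic is 1.54 at 40/50 (below 1.645) and 1.85 at 41/50.

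Below 70%, the 36/50 cut-off passes with probability 18.8% at a true 65% and 5.4% at 60%.

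**3. Where the readings disagree.** Counts of 36 to 40 meet the written definition but fail the exact one-sided test. P(36 ≤ X ≤ 40) at a true 85% is 0.9947 − 0.7911 = 20.4%. At 80% it is 49.6%, and at 75% it is 58.4%.

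**4. Confidence limits.** The exact 90% interval at 41/50 is 70.7% to 90.3%, which excludes 70% in agreement with the exact one-sided test. At 40/50 the lower limit is 68.4%, which does not.

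**The case against.** The strongest reply is that the sentence is labelled a hypothesis. More than 70% can then be the alternative about the true rate, with section 9.2 supplying the test parameters. On that reading there is one under-specified rule, not two conflicting ones. This stands as a possible reading, and a reader who infers a proven contradiction goes further than the text allows. It does not rescue the plan: the sentence also says that feasibility is defined this way and counts subjects, section 4.2 gives a bare 70% rate, and on either reading the required count is missing.

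Three other strong inferences should be resisted.

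- That the sample size is wrong. It is not; step 1 reproduces it.
- That the power claim proves a one-sided test needing exactly 41. It does not. A two-sided 95% Wald interval is also first satisfied at 41/50, with the same 79.1% power, and the normal approximation is the interval method section 9.3 specifies for complete response. Other tests give 40 or 42. None passes at 36.
- That 44.7% is an error rate without qualification. It is one only if a true rate of exactly 70% counts as not feasible. The wording in section 2.1 implies that, whereas section 9.2 calls 70% acceptable. The same condition applies to the 56.9% for 35/50. The 99.5% at a true 85% is not a defect in itself; it shows only that the 80% figure belongs to another rule.

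The consequence is also softer than it could be. Section 5.3 describes future plans, the secondary analyses in section 9.3 are not made conditional on feasibility, and no efficacy claim depends on the primary outcome.

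**Conclusion.** The concern holds in a conditional form. The plan attaches a Type I error and a power to a primary conclusion without stating the rule that produces it. If the definition is an observed cut-off, as literally worded, it is met at 36/50 and passes 44.7% of the time at a true 70% and 18.8% at 65%, not 5%. If it is a hypothesis about the true rate, the stated figures fit a test against 70% with a cut-off near 41/50 that appears nowhere in the documents. The gap of 36 to 40 completers has probability 20.4% under the plan's own 85%, and about half or more at 80% and 75%.

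This assumes 50 subjects in one pooled denominator, independent completion, and the exact one-sided test as the comparator. The cut-off shifts by one either way with other tests; the conclusion about 36/50 does not change. It should be settled before the data are seen, because it can reverse the primary conclusion and costs little to correct.

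**What to change.** Use one rule, in the same words, in the synopsis and sections 2.1, 4.2 and 9.2.

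- Preferred, because it matches the stated power: H0: p ≤ 0.70 against H1: p > 0.70, exact one-sided binomial test at 0.05 on all 50 enrolled subjects pooled; feasibility is concluded if at least 41 complete all study procedures (size 0.040, power 79% at a true 85%). Report the completion rate with an exact 90% confidence interval. If the number of subjects differs from 50, apply the same test to the actual number.
- Alternative: keep the observed cut-off, say whether exactly 35/50 passes, and replace the Type I error and power claim with that rule's own probabilities (for 36/50: 44.7% at a true 70%, 18.8% at 65%, 99.5% at 85%).

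Two secondary clarifications belong in the same edit: who the selected study subjects in section 2.1 are, given that section 4.1 enrols 50; and whether the reference to chemotherapy and tumour strata in section 9.2 implies a rule per stratum. The calculation for 50 subjects supports only a pooled rule.

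The cost is wording, with no extra patients. The preferred rule makes the bar visibly higher, at 82%; the alternative gives up the 5% and 80% figures.
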